RTMS THERAPY: Real stimulation: Repetitive-TMS will be delivered sequentially over each cerebellar hemisphere, using Neuronetics NeuroStar Transcranial Magnetic Stimulation (TMS) FDA approved TMS Therapy device. Neurostar coil will be positioned over a point that is 3 cm lateral to the inion on the line joining the inion and the external auditory meatus. The coil position will be marked on the skin. The current in the coil is directed downward, which will in effect induce an upward current in the cerebellar cortex. 900 pulses will be delivered consecutively to each side with a frequency of 1 Hz and at an intensity of 90% of the resting motor threshold (RMT) for a total duration of 15 min for each cerebellar hemisphere. The RMT will be defined as the lowest stimulation intensity required to evoke a $50\text{ }\mu\text{V}$ potential in a target muscle (i.e. first dorsal interosseous muscle in our case). Constant coil position will be continuously monitored during the experiment. During rTMS, all patients will wear ear plugs in order to protect the ears from the acoustic artefact associated with the discharge of the stimulation coil. Similar protocol will be observed for the contralateral cerebellum. The electrical field induced by this coil is maximal beneath the center of the figure-of-eight coil.²⁵ Use of this type of coil stimulates a small area of the cortex of approximately 2 cm in diameter. It is presumably unlikely that the coil placed over the occiput will stimulate structures much deeper than 2 cm.²⁶ This means the cerebellum (at least 1.5 cm deep) will preferentially be stimulated rather than the brainstem (at least 3.0 cm deep).^{26,27} The inion will be taken as a landmark of the boundary between the posterior cerebellum and the occipital cortex. We therefore will stimulate the area caudal to the inion to stimulate the posterior cerebellum.²⁸

[figure not shown]

Figure 3: Figure-of-eight coil is placed 3 cm lateral to the inion on the line joining inion and external auditory meatus. The coil will then be placed on the opposite side for stimulation

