Sham Stimulation: Patients randomized to receive sham treatment will undergo the same procedure for identifying stimulus location used in patients receiving real rTMS. Simulated rTMS will be administered using Magstim Placebo 70 mm figure-of-eight shaped coil which produces discharge noise and vibration similar to a real 70 mm coil without stimulating the cerebral cortex. However, in addition to obvious coil discharge noise, rTMS also causes electrical stimulation of the scalp. We will simulate this experience by attaching surface electrodes underneath the sham coil and in contact with the scalp. We will use an electromyography to administer electrical shocks to the scalp simultaneous to each simulated rTMS train. This technique has been suggested to provide more effective blinding compared to other methods use in previous controlled studies.²⁹

Possible Discomfort and Risks: The main risk involved in TMS is the very rare possibility of triggering seizures. Magnetic stimulation treatment may be associated with some transient discomfort in the scalp. Typically, a twitching sensation is experienced. Some patients have complained of headache, dental and neck pain. These problems may be treated with over-the-counter medications such as Tylenol or Advil. Because of noise produced by magnetic coils, we will supply earplugs that participants may wear during magnetic stimulation treatments, in order to protect the hearing of the subjects. Repetitive TMS can have undesired side effects.²⁵ Guidelines for the safe use of rTMS were formulated at the 1st International Workshop on the Safety of TMS.³⁰ These were adopted by the International Federation for Clinical Neurophysiology and subsequently updated.³¹ The proposed study will use TMS parameters well within the published safety guidelines. We will conduct careful monitoring of the participants and follow all recommended precautions for the application of TMS.

Women of childbearing age will have a urine pregnancy test to evaluate for pregnancy.

Possible Benefits: There will not be any direct benefits to the patients. This study will improve our understanding of the primary orthostatic tremor and the potential treatments.

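### Scalp electrodes are described only for the sham session and nothing hides the rTMS equipment from the patient, which leaves avoidable cues in a crossover called double blind

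*Combined protocol and SAP*

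**What the plan says.** Goal and Specific Aims describes a double-blind, placebo-controlled crossover in twenty patients. Under Study design, each patient has one real and one sham session on different days, in counterbalanced order.

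Real stimulation is given "using Neuronetics NeuroStar Transcranial Magnetic Stimulation (TMS) FDA approved TMS Therapy device", with the coil 3 cm lateral to the inion, first on one side and then on the other. That paragraph covers coil position, skin marking, current direction, pulse number, intensity and ear plugs. It mentions no scalp electrodes.

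Under Sham Stimulation, patients "will undergo the same procedure for identifying stimulus location used in patients receiving real rTMS". The sham coil is a Magstim placebo coil that "produces discharge noise and vibration similar to a real 70 mm coil". The plan notes that "rTMS also causes electrical stimulation of the scalp" and imitates it: "We will simulate this experience by attaching surface electrodes underneath the sham coil and in contact with the scalp". Shocks are then delivered in time with the simulated trains. The paragraph closes by citing a source for the view that this technique blinds better than methods used in earlier controlled studies.

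Clinical assessments states that the physician giving TMS knows the allocation, that outcome assessors stay out of the TMS sessions, and that videos go to a blinded rater. No section describes hiding the rTMS equipment from the patient or checking the patient's blind.

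**The concern.** The treating physician is unblinded by design, so the double-blind label rests on the assessors and the patient. The assessors are covered by explicit procedures. The patient is covered by the sham technique alone, and as written that technique gives the two days different set-ups: electrodes fixed to the scalp on one day and, as far as the text goes, none on the other. In a parallel-group trial a patient has nothing to compare with. Here each patient experiences both.

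If some patients tell the days apart, expectation can alter what they do or report. TUG and the 10 m walk are timed performances and depend on effort. Total TRS is exposed too if it includes the patient-reported Part C, but Clinical assessments does not say which parts make up the total. Blinded scoring protects the rating and not the patient's own effort or report. The leg tremor score (a motor item scored from video by a blinded rater), EMG and CBI are less exposed.

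**Working it through.** **Step 1. Compare the two sessions as written.**

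| Feature | Real session | Sham session | Equalised? |
|---|---|---|---|
| Site-finding | described | same procedure | yes |
| Scalp sensation | produced by real rTMS | imitated by shocks | attempted |
| Electrodes on scalp | none described | under the coil | no |
| Noise and vibration | NeuroStar coil | likened to a real 70 mm coil | not stated |
| Equipment hidden from patient | not described | not described | no step |
| CBI with Magstim equipment | T0, T1, T2 | T0, T1, T2 | yes |

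The differences that remain are the electrodes, an unstated acoustic match and equipment in view.

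**Step 2. Is there a figure to reproduce?** No. The documents give no SD, effect size, power or sample-size derivation, so the size of any bias cannot be derived from them.

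**Step 3. Illustration on assumed values.** From the documents: n = 20 (Goal and Specific Aims) and two-sided α = 0.05 (Statistical analysis). Assumed: a paired t-test on the real-minus-sham difference in place of the planned mixed model, no true effect, SD of the difference 1, and each patient independently shifted by s with probability p, otherwise not at all.

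- Mean of the difference = p·s
- SD of the difference = √(1 + s²·p·(1−p))
- Noncentrality = √20 × mean / SD
- Rejection if |t| > 2.093 (19 degrees of freedom)

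For p = 0.2 and s = 0.5: mean 0.100, SD √(1 + 0.25 × 0.16) = 1.020, noncentrality 4.472 × 0.100 / 1.020 = 0.44, rejection 7.0%.

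| Share shifting, all in one direction | Rejection, s = 0.5 SD | Rejection, s = 0.2 SD |
|---|---|---|
| 0% | 5.0% | 5.0% |
| 20% | 7.0% | 5.3% |
| 30% | 9.5% | 5.7% |
| 50% | 17.7% | 7.1% |
| 100% | 56.5% | 13.6% |

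Simulation of the same model agrees with each entry to within about 0.1 percentage points. Opposite shifts cancel: if every patient shifts by 0.5 SD but the directions split 75:25, rejection is 16.8%; at 50:50 it is 5.0%.

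**Step 4. What a treatment guess could show.** If 10 of 20 patients guess the real day correctly, the exact (Clopper-Pearson) 95% interval is 27.2% to 72.8%. That describes the guesses and cannot establish that the blind held.

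**Step 5. Room for pads.** The real-stimulation paragraph says "This means the cerebellum (at least 1.5 cm deep) will preferentially be stimulated" and puts the coil's likely reach at about 2 cm. The margin is therefore at most about 2.0 − 1.5 = 0.5 cm, so anything that lifts the active coil off the scalp matters.

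**The case against.** The strongest reply is that the electrodes are themselves the blinding measure. The plan chose them to reproduce a sensation that real rTMS causes, and it cites support for that choice. The source is not available here, so nothing can be said against the technique. This stands: the shocks are a strength, and the point is only that their hardware is described for one day.

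Three further replies stand in part.

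- The real-session text is silent about electrodes and does not exclude them. If they are used on both days, one sentence settles that item.
- The coil sits behind the head, so little is visible during stimulation. Electrodes can still be felt, the coil heard, and equipment seen during set-up.
- Noticing a difference is not the same as knowing which day is sham.

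A reader might infer more than the documents support:

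- **That different coil makers give the sham day away.** Magstim equipment is used for CBI on both days, so the maker's name marks neither. Only the unstated match in noise and vibration remains.
- **That ear plugs are a cue.** One paragraph says "all patients will wear ear plugs", while the risk section says "we will supply earplugs that participants may wear during magnetic stimulation treatments". The two need reconciling, but neither statement distinguishes real from sham.
- **That Part C is certainly in total TRS.** The components of the total are not defined, and patient-reported disability cannot be scored from the videotaped items.

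**Conclusion.** The point holds as a limited design weakness. As written, the two days differ in ways that cheap steps could reduce, and each patient is able to compare them. TUG and the 10 m walk are exposed, and possibly total TRS. Blinded assessors and video rating, together with EMG and CBI, limit the damage.

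Neither the size nor the direction of any bias can be derived. The illustration rests wholly on an assumed shift, an assumed share of patients and a paired t-test. It runs from no inflation to 56%. The top figure needs every patient to shift by 0.5 SD in the same direction; with 20% to 30% shifting it is about 7% to 9.5%. It would be wrong to read 56% as a forecast, or to conclude that patients will recognise the sham day or that the trial is not blind: nothing in the documents shows this. Priority: minor to moderate.

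**What to change.** Amend the Real stimulation and Sham Stimulation paragraphs as follows.

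1. Keep the rTMS coil, stimulator and electrode leads out of the patient's sight during set-up and stimulation on both days.
2. Leave the sham electrodes as planned, so that the simulated sensation is not weakened. On the real day apply inert, look-alike, non-conductive pads near the same site, outside the active coil's contact area so that coil-to-scalp distance is unchanged, after checking compatibility with the active coil.
3. Ask each patient once, after the last assessment of the second session, which day they believe was real. Report the answers descriptively only.

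Minor clarifications: state whether the sham coil's noise and vibration match the NeuroStar coil, which hiding the equipment does not address; reconcile the two ear-plug statements; and say whether Part C counts towards total TRS.

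The cost is protocol wording, a screen, pads, a compatibility check and a few minutes of set-up. The pads will match the electrodes only approximately. A late guess cannot prompt comparison before outcomes are recorded, but it is mixed up with felt benefit and is imprecise with 20 patients. Outcomes, analysis, sample size and stimulation settings stay as they are, and a matched coil pair is not required.

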This proposal is significant because the approach is novel, innovative and promising. The findings of this study will be the first step towards development of a reliable and effective treatment for POT. In addition, the TMS related physiology will shed further insights into the pathophysiology of POT and the mechanisms underlying treatment response.

GOAL AND SPECIFIC AIMS:

The **primary goal** of this study is to test the efficacy of low frequency rTMS therapy in POT. In this one year application, we expect to enroll twenty POT patients using a double blind randomized placebo controlled crossover design. We will enroll POT patients from our large research database (IRB approved protocol 416-2002) in addition to screening outpatient clinics. We plan to obtain IRB approval over the next few months while the grant is undergoing review process. Once the study is initiated, we will collect the data over the first six months. We will then plan for data analysis and publication over the subsequent six months. We believe the pilot findings from this study will be used for development of a larger multicenter clinical trial.

The **specific aims** of the proposal are:

Aim 1: To determine the clinical impact of 1-Hz rTMS therapy in POT when delivered to the cerebellum. This impact will be evaluated by the clinical scoring of leg tremors in standing posture, and the functional assessment of gait mobility. Comparisons will be drawn between T0 (before rTMS therapy), T1 (immediately or +5 minutes after) and T2 (60+ minutes after) assessments to determine the time course of effects.

Hypothesis: 1-Hz rTMS therapy will result in clinical improvement of leg tremors and gait mobility in POT. In addition improvement in scores at T1 assessment will be greater than those recorded at T2 assessment.

Aim 2: To determine the physiological effects of 1-Hz rTMS therapy in POT when delivered to the cerebellum.

Aim 2a: We will determine the effects on the amplitude and frequency of tremors recorded with surface EMG. Comparisons will be drawn between T0, T1 and T2 assessments. **Hypothesis:** 1-Hz rTMS therapy will reduce the amplitude of tremors and will have no effects on the frequency of tremors. The amplitude reduction in tremors will be greater at T1 assessment than at T2 assessment.

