Statistical analysis: The primary outcome measures in this study are change in total TRS score, leg tremor score, TUG test speed, 10m walk test time. The secondary outcome measures are amplitude and frequency of tremors on the surface EMG and the CBI recorded. Data will be presented as mean (SD) unless otherwise indicated. Each dependent measure will be examined using the following statistical approach. For each of the outcome variables, we will conduct a mixed model analysis using time and stimulation arm as repeated factors adjusted for baseline values, and subjects as the random factor. The model will include 2 within-subject factors: treatment (2 levels: active vs sham) and time (3 levels: T0, T1, and T2). If the interaction effects between stimulation arm and time are non-significant, they will be dropped. In case of significant main effects, post hoc pairwise comparisons will be corrected using Fisher least significant difference procedure in accordance with the closed test principle; i.e., post hoc comparisons will be declared non-significant if the global *p* value of the main effect (testing equality of all 2 stimulation arms simultaneously) are non-significant, but will be carried out without further correction in case of a significant global main effect. SPSS version 15.0 for Windows will be used for statistical computations. The 2-tailed significance level will be set at 0.05

The University of Florida nor the Principal Investigator hold a patent or license for any material, object or process used in this study. There is no license pending or under consideration or is there any intention to file a patent application at a later date.

Computer-based files will only be made available to personnel involved in the study through the use of access privileges, passwords and encryption. Passwords and encryption are used to ensure that the electronic data is secure and housed in a locked room.

Videos are edited in a secure research lab then the edited videos are deposited into a secured server in the University of Florida Health Science Center server. Access to the server and the videos on its restricted drive are limited to a directory group who need access to the movement disorders clinic or research videos on it

Data Safety Monitoring Plan

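### Four unranked primary outcomes are each tested at two-sided 0.05 with no rule across them; if any one counts as efficacy, the false-positive chance is about 9–19%

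*Combined protocol and SAP*

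**What the plan says.** All the relevant rules are in the Statistical analysis section. It names four primary outcomes in one unranked list: "The primary outcome measures in this study are change in total TRS score, leg tremor score, TUG test speed, 10m walk test time". It then says "Each dependent measure will be examined using the following statistical approach", namely a mixed model with treatment (active, sham) and time (T0, T1, T2) as within-subject factors. The error level is given once: "The 2-tailed significance level will be set at 0.05".

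The only multiplicity provision is Fisher's least significant difference procedure, justified by the closed test principle. Post hoc comparisons are made only if the main effect is significant, and then "will be carried out without further correction in case of a significant global main effect".

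Under Goal and Specific Aims, the primary goal "of this study is to test the efficacy of low frequency rTMS therapy in POT". The Aim 1 hypothesis is that "1-Hz rTMS therapy will result in clinical improvement of leg tremors and gait mobility in POT", and that "improvement in scores at T1 assessment will be greater than those recorded at T2 assessment". The same section adds: "We believe the pilot findings from this study will be used for development of a larger multicenter clinical trial".

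**The concern.** The plan tests efficacy on four measures and does not say what pattern of results would count as success. It gives no alpha split, no hierarchy and no requirement that several outcomes succeed together.

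The Fisher procedure does not fill the gap, because it is applied within one outcome at a time. With only two arms, its global test of stimulation arm is already the single active-versus-sham comparison, so it gives no protection across outcomes.

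As the text stands, one p<0.05 among four could be reported as a positive primary result, and 0.05 would not be the error rate of that claim. A chance finding could then steer the choice of endpoint in the larger trial that this study is meant to inform.

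**Working it through.** The plan states no family-wise error rate or power, so there is no figure of its own to reproduce.

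**Inputs from the documents.** Four primary outcomes; two-sided 0.05 per test; a planned enrolment of 20 in a two-session crossover.

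**Assumptions.** One active-versus-sham test per outcome; test statistics jointly normal with a common correlation ρ; no true effect on any outcome unless stated. The documents give no correlations, so ρ runs from 0 to 0.9.

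**Any one of four.** With independent outcomes, 1 − (1 − 0.05)⁴ = 1 − 0.8145 = 0.1855. Under any dependence the upper bound is 4 × 0.05 = 0.20. For correlated outcomes the quantity is 1 − P(all four |Z| < 1.96), where

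P(all k inside c) = ∫ φ(t) [Φ((c − √ρ·t)/√(1−ρ)) − Φ((−c − √ρ·t)/√(1−ρ))]ᵏ dt, with k = 4 and c = 1.96.

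**Aim 1 wording used as a rule.** Suppose success needs at least one significant tremor result (total TRS or leg tremor) and at least one significant gait result (TUG or 10 m walk). With I₂ and I₄ the probabilities that two or all four statistics stay inside ±1.96, the chance is 1 − 2·I₂ + I₄. At ρ = 0 this is 1 − 2(0.9025) + 0.8145 = 0.0095.

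**Either gait test falsely significant.** 1 − I₂; at ρ = 0 this is 1 − 0.9025 = 0.0975.

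**Holm.** When nothing works, any rejection requires the smallest p to be at or below 0.05/4 = 0.0125. At ρ = 0 the chance is 1 − (1 − 0.0125)⁴ = 0.049. For other ρ the integral above is used with c = 2.498.

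| ρ | Any of 4 at 0.05 | ≥1 tremor and ≥1 gait | Either gait test | Holm, any of 4 |
|---|---|---|---|---|
| 0 | 18.5% | 1.0% | 9.8% | 4.9% |
| 0.3 | 17.4% | 1.6% | 9.5% | 4.7% |
| 0.5 | 15.6% | 2.6% | 9.1% | 4.3% |
| 0.7 | 13.0% | 3.7% | 8.3% | 3.7% |
| 0.8 | 11.4% | 4.2% | 7.8% | 3.2% |
| 0.9 | 9.4% | 4.7% | 7.0% | 2.6% |

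**Check with the planned n.** Simulated paired t tests with n = 20 (400,000 replicates per ρ) gave 18.6%, 15.7% and 9.7% for any of four at ρ = 0, 0.5 and 0.9. An unequal pattern (0.8 within the tremor pair and within the gait pair, 0.3 between pairs) gave 14.6%.

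**Power cost of Holm.** Assume 20 completers, a paired t test with 19 df, and only one outcome that moves. The noncentrality is d√20. At d = 0.66 it is 2.95. Power is 80% against the critical value 2.093 (alpha 0.05) and 58% against 2.759 (alpha 0.0125). Recovering about 80% at 0.0125 needs d = 0.81.

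**The case against.** The strongest reply is that the plan never says one significant result is enough. The only hypothesis put into words joins tremor and gait, and read as a decision rule it has an error of 1.0–4.7% when nothing works. If all four outcomes had to succeed, the error could not exceed 5%. This stands to the extent that the 9–19% is conditional on the any-one reading. It does not remove the problem, because Aim 1 states a hypothesis and the Statistical analysis section does not turn it into a rule. Even under the Aim 1 rule, if tremor truly improves and gait does not, the false gait finding approaches 7.0–9.8%. That range is an upper bound, reached only when a tremor result is certain to be significant.

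Second, independence is implausible. The leg tremor score is taken from a TRS item, and TUG and the 10 m walk both assess gait, so the top of the range is unlikely. That is fair. The unequal pattern above still gives 14.6%, and a correlation of 0.9 throughout still gives 9.4%.

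Third, the figures count one test per outcome, whereas the plan also tests an interaction, main effects and post hoc contrasts. This limits precision. The extra tests could raise the true rate.

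Fourth, this is a study of 20 patients with a rare disorder, its findings are called pilot findings, and all four outcomes are named in advance. That lowers the consequence. But the tests are not labelled exploratory, and the stated goal is to test efficacy.

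**Conclusion.** The concern holds. The plan has no decision rule across its four primary outcomes, and its closed-test wording does not provide one. If any single p<0.05 is accepted as efficacy, the false-positive chance is about 9–19% for assumed common correlations from 0.9 down to 0, with one active-versus-sham test per outcome. Other readings that the text leaves open give an error of 5% or less when nothing works, so the rate depends on a choice that could be made after the data are seen. This should be corrected. It does not call the design into question, and the pilot purpose limits the damage.

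**What to change.** Add a few lines to the Statistical analysis section, choosing one of three options. None changes visits, measures or sample size.

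1. **Holm across the four.** Define one active-versus-sham contrast per primary outcome and apply Holm at an overall two-sided 0.05. Change from T0 to T1 is a candidate contrast: Aim 1 expects the larger effect at T1, and the visit schedule has all four measures there. The smallest p must then be at or below 0.0125, with the power loss shown above if only one outcome moves and a smaller loss if several do. The T2 data would fall outside the primary test.

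2. **One pre-named primary outcome, the other three ranked as secondary.** Leg tremor in standing posture, which Aim 1 lists first, is a candidate; the choice is the investigators'. Power stays at the 0.05 level, but a result on another measure alone would no longer be a primary success. A single item scored 0–4 is coarse, and ties are likely.

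3. **Exploratory label.** Call the four tests exploratory and report all four estimates with confidence intervals. This fits the pilot purpose and needs no stricter threshold, but the study could not then claim a confirmatory test of efficacy, and the wording of the primary goal should be changed to match.

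### The closed-test claim for the post hoc comparisons does not hold: the global test compares only the two arms, while the comparisons the aims need run over T0, T1 and T2

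*Combined protocol and SAP*

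**What the plan says.** The Statistical analysis section of the combined protocol and SAP sets out a two-by-three repeated-measures model: "The model will include 2 within-subject factors: treatment (2 levels: active vs sham) and time (3 levels: T0, T1, and T2". A non-significant arm-by-time interaction is to be removed. Follow-up testing is described as "post hoc pairwise comparisons will be corrected using Fisher least significant difference procedure in accordance with the closed test principle". The global test that controls entry to the follow-up is described as "testing equality of all 2 stimulation arms simultaneously". If it fails, the post hoc comparisons are declared non-significant. If it succeeds, they "will be carried out without further correction in case of a significant global main effect". On the level, the plan says "The 2-tailed significance level will be set at 0.05".

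The section does not list the post hoc comparisons, and it does not say what follows a significant interaction. Aim 1 states what is wanted: "Comparisons will be drawn between T0 (before rTMS therapy), T1 (immediately or +5 minutes after) and T2 (60+ minutes after) assessments". It also hypothesises more improvement at T1 than at T2. Aims 2a and 2b ask for the same three time points.

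**The concern.** Fisher's procedure is a closed test for three means when their own three-level global test comes first. Here the global test has two levels and one degree of freedom, so nothing remains to be compared between arms afterwards. The comparisons the aims need are among times, or between arms at a given time, and a test of equal arm means is not a test of their joint null. The stated protection is therefore absent for them.

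Two things are at stake. A real arm effect may admit a set of uncorrected time comparisons, some of them true nulls. In the other direction, a real effect confined to T1 may be declared non-significant because the arm test averages it with T0, where no effect can exist, and T2. The Background makes that pattern plausible: in the cited essential tremor study, benefit after cerebellar stimulation seemed to be gone at one hour. The pilot is meant to inform a larger trial, so its time-course conclusions matter.

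**Working it through.** The plan states no familywise error rate and no power, so there is no figure to reproduce.

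**Inputs from the documents:** 20 subjects in a crossover; 2 arms by 3 times; two-sided 0.05; a global test on arms; no correction afterwards.

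**Assumptions:** normal data, error SD 1, visit SD v of 0 or 0.5, no missing data, no baseline covariate (T0 is already a time level), no change over time under sham. Simulations used 20,000 trials per setting.

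**1. Nothing works.** The arm test passes in about 5% of trials, which caps the error for any family behind it at about 5%. Simulated: 0.7% for three pooled time pairs, 1.2% for six within-arm pairs, 4.3% for all 15 pairs of cells.

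**2. A real arm effect, three pooled time pairs, all null.** Error df = (20 − 1) × (6 − 1) = 95. The chance that at least one of three unadjusted pairs is significant is P(studentized range for 3 means > √2 × t(0.975; 95)) = 12.1%. For independent tests it would be 1 − 0.95³ = 14.3%. This is a ceiling: all three pooled nulls must be true. With a T1-only effect only T0 versus T2 is null, and the rate is about 5%.

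**3. A T1-only effect of d error SD, nine contrasts.** There are 3 active-sham contrasts and 2 × 3 = 6 within-arm contrasts. Three are truly non-null: active-sham at T1, active T0–T1 and active T1–T2. Six are null: active-sham at T0 and at T2, active T0–T2, and three under sham. The table gives the chance that the arm test passes, and the chance that it passes and at least one of the six nulls is significant.

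| d | v | Arm test passes | At least one false claim |
|---|---|---|---|
| 1.0 | 0 | 41% | 10% |
| 1.0 | 0.5 | 26% | 7% |
| 1.5 | 0 | 74% | 16% |
| 1.5 | 0.5 | 50% | 11–12% |
| 2.0 | 0 | 93% | 20% |
| 2.0 | 0.5 | 75% | 16% |
| 3.0 | 0 | 100% | 22% |
| 3.0 | 0.5 | 97% | 21–22% |

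In the settings that give 16–22%, a false active-sham claim at T2 occurs in 3–5% of trials. The three sham-only time pairs contribute most (9–12%).

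**4. Dilution of a T1-only effect, d = 1.0.** The arm test sees d/3, and its noncentrality is √20 × (d/3) / √(2(v² + 1/3)).
- v = 0: 4.472 × 0.333 / 0.816 = 1.83, power 41%.
- v = 0.5: 4.472 × 0.333 / 1.080 = 1.38, power 26%.

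The T1 contrast has noncentrality √20 × d / √(2(v² + 1)).
- v = 0: 4.472 / 1.414 = 3.16, power 85%.
- v = 0.5: 4.472 / 1.581 = 2.83, power 76%.

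The chance that both tests are significant is 40% (v = 0) and 25% (v = 0.5).

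**The case against.** The strongest reply is that the plan can be read more kindly. It says "In case of significant main effects, post hoc pairwise comparisons will be corrected using Fisher least significant difference procedure", in the plural, and time is also a main effect. If the three-level time effect controls three pooled time pairs, that is ordinary LSD, and simulation gives 4.8–5.3%. The reading is possible. However, the only global test the sentence defines is the one on arms. A pooled time test also leaves within-arm comparisons unprotected: with a real active effect they still run at about 12–17%.

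Second, a T1-only effect is an interaction, and the LSD sentence concerns main effects. In the settings giving 16–22% the interaction is significant in over 92% of trials. If only trials that pass the arm test and drop the interaction are counted, the rate over the same six nulls is at most about 4%. This stands as a limit on the size. It also exposes a gap, because the plan has no follow-up rule for the interaction its own hypotheses predict.

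Third, a reader might infer that each outcome carries a 16–22% false-positive rate, or that false claims of benefit at T2 run at several times 5%. The documents support neither. The nine-contrast family is not in the plan, and the required effects are large. Most of the excess comes from sham-only comparisons, which are not efficacy claims.

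**Conclusion.** The closed-test statement is wrong as written for the comparisons in the aims. That conclusion rests on the text alone and needs no simulation.

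The size is conditional. Within one outcome the error is at most about 5% under the global null, and up to about 12% for three pooled time pairs once a real arm effect has passed the arm test. It is 16–22% only if all nine contrasts are tested and a T1-only effect of about 1.5–3 error SD passes the arm test; the lower end needs about 2 SD when visit SD is 0.5. At 1.0 SD it is 7–10%. The loss of power at T1, from 76–85% to 25–40% at 1.0 SD, is at least as serious for a pilot.

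The documents give no effect size or variance, so these ranges depend on the assumptions listed with the calculation. Multiplicity across the four primary outcomes is a separate matter and is not counted here.

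**What to change.** Replace the LSD and closed-test sentence. For each outcome, test active minus sham at T1 at two-sided 0.05. Only if that is significant, test both of the following, each at 0.05:

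- (a) active minus sham at T2;
- (b) the difference between the active-sham effects at T1 and at T2.

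Write δ1 and δ2 for the active-sham effects at T1 and T2. If δ1 = 0, the first test limits the error to 5%. If δ1 ≠ 0, the nulls δ2 = 0 and δ1 = δ2 cannot both be true, so at most one of (a) and (b) can be a false claim. The procedure therefore holds 5% per outcome.

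Do not make the T2 test wait on (b). With equal effects of 1.0 SD at T1 and T2, that order would claim T2 in only about 1–2% of trials, against 60–72% when T2 follows T1 directly.

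Keep the arm-by-time term for these contrasts whatever its p value; without it the arm difference is the same at every time and (b) does not exist. Report T0–T1–T2 changes within each arm with confidence intervals and no significance claims.

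The cost is SAP wording. T2 gets no formal test if T1 fails, and within-arm changes become descriptive.
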